12.3 Collaborative Agreements Language

The agent(s) supplied by CTEP, DCTD, NCI used in this protocol is/are provided to the NCI under a Collaborative Agreement (CRADA, CTA, CSA) between the Pharmaceutical Company(ies) (hereinafter referred to as "Collaborator(s)") and the NCI Division of Cancer Treatment and Diagnosis. Therefore, the following obligations/guidelines, in addition to the provisions in the "Intellectual Property Option to Collaborator" (http://ctep.cancer.gov/industryCollaborations2/intellectual_property.htm) contained within the terms of award, apply to the use of the Agent(s) in this study:

1. Agent(s) may not be used for any purpose outside the scope of this protocol, nor can Agent(s) be transferred or licensed to any party not participating in the clinical study. Collaborator(s) data for Agent(s) are confidential and proprietary to Collaborator(s) and shall be maintained as such by the investigators. The protocol documents for studies utilizing Agents contain confidential information and should not be shared or distributed without the permission of the NCI. If a copy of this protocol is requested by a patient or patient's family member participating on the study, the individual should sign a confidentiality agreement. A suitable model agreement can be downloaded from: <http://ctep.cancer.gov>.
2. For a clinical protocol where there is an investigational Agent used in combination with

(an)other Agent(s), each the subject of different Collaborative Agreements, the access to and use of data by each Collaborator shall be as follows (data pertaining to such combination use shall hereinafter be referred to as "Multi-Party Data"):

- a. NCI will provide all Collaborators with prior written notice regarding the existence and nature of any agreements governing their collaboration with NCI, the design of the proposed combination protocol, and the existence of any obligations that would tend to restrict NCI's participation in the proposed combination protocol.
- b. Each Collaborator shall agree to permit use of the Multi-Party Data from the clinical trial by any other Collaborator solely to the extent necessary to allow said other Collaborator to develop, obtain regulatory approval or commercialize its own Agent.
- c. Any Collaborator having the right to use the Multi-Party Data from these trials must agree in writing prior to the commencement of the trials that it will use the Multi-Party Data solely for development, regulatory approval, and commercialization of its own Agent.

3. Clinical Trial Data and Results and Raw Data developed under a Collaborative Agreement will be made available to Collaborator(s), the NCI, and the FDA, as appropriate and unless additional disclosure is required by law or court order as described in the IP Option to Collaborator (http://ctep.cancer.gov/industryCollaborations2/intellectual_property.htm). Additionally, all Clinical Data and Results and Raw Data will be collected, used and disclosed consistent with all applicable federal statutes and regulations for the protection of human subjects, including, if applicable, the *Standards for Privacy of Individually Identifiable Health Information* set forth in 45 C.F.R. Part 164.
4. When a Collaborator wishes to initiate a data request, the request should first be sent to the NCI, who will then notify the appropriate investigators (Group Chair for Cooperative Group studies, or PI for other studies) of Collaborator's wish to contact them.
5. Any data provided to Collaborator(s) for Phase 3 studies must be in accordance with the guidelines and policies of the responsible Data Monitoring Committee (DMC), if there is a DMC for this clinical trial.
6. Any manuscripts reporting the results of this clinical trial must be provided to CTEP by the Group office for Cooperative Group studies or by the principal investigator for non-Cooperative Group studies for immediate delivery to Collaborator(s) for advisory review and comment prior to submission for publication. Collaborator(s) will have 30 days from the date of receipt for review. Collaborator shall have the right to request that publication be delayed for up to an additional 30 days in order to ensure that Collaborator's confidential and proprietary data, in addition to Collaborator(s)'s intellectual property rights, are protected. Copies of abstracts must be provided to CTEP for forwarding to Collaborator(s) for courtesy review as soon as possible and preferably at least three (3) days prior to submission, but in any case, prior to presentation at the meeting or publication in the proceedings. Press releases and other media presentations must also be forwarded to CTEP prior to release.

Copies of any manuscript, abstract and/or press release/ media presentation should be sent to:

Email: [contact]

The Regulatory Affairs Branch will then distribute them to Collaborator(s). No publication, manuscript or other form of public disclosure shall contain any of Collaborator's confidential/ proprietary information.

13. STATISTICAL CONSIDERATIONS

13.1 Study Design/Endpoints

This will be a phase 1b study [schema]. The proposed dosing of ENT has been previously tested in MDS and showed to be well-tolerated. While the combination of ENT with the anti-PD1, Pembrolizumab (MK-3475) has not been studied clinically in MDS patients, it is unlikely that this combination would have overlapping toxicities.

PART 1: ENT has been previously evaluated as a single agent therapy in patients with MDS at these doses and has been well tolerated. The ENT monotherapy run-in part (cycle 1) will allow to study the changes in myeloid derived suppressor cells (MDSCs) at pre- and post-ENT treatment (the end of cycle 1) to dissect the effects of ENT monotherapy from those of the combined ENT/anti-PD1 therapy.

We will perform '3+3' classical dose escalation design to determine dose limiting toxicity (DLT). The first 3 patients will receive ENT at dose level 1 (DL1: 8mg on D1, 8 of 21-day cycles). Pembrolizumab (MK-3475) will be added starting day 1 cycle 2 at the approved dose of 200mg intravenously [IV] over 30 minutes on D1 of 21-day cycles for 4 cycles. A safety committee that includes the study chair, the principal investigator from any study site that has enrolled a patient on the specific DL, as well as two sub-investigators from Yale will review safety data after enrollment of every 3 patients during the dose escalation phase. The committee will have the discretion to decide to enroll 3 more patients in the specific dose level even if no DLT occurred in the first 3 treated patients in that dose level if there are toxicity/safety concerns that did not qualify as DLT (maximum of 6 evaluable patients to be enrolled at any dose level). The committee can also decide to enroll patients at a lower dose level after the first 3 or after the first 6 patients enrolled in any dose level even if no or one DLT occurred at that dose level if there are toxicity/safety concerns that did not qualify as DLT. The following regarding enrollment in different dose levels will be considered guidance for the safety committee but can be modified in accordance of above: If no patient of the 3 patients treated with combined therapy at DL1 develops DLT, then dose level 2 (DL2) will be tested. For instance, DL2 will be with ENT at 8mg on D1, 8 and 15 and MK-3475 (pembrolizumab) at 200mg IV on D1 of 21-day cycles. If 1 patient out of the 3 patients has DLT at DL1, we will expand cohort to 3 more patients and if 1 patient of the 6 patients has DLT (i.e. only 0/3 or 1/6), we will test next dose (DL2). If no patient of the 3 patients treated with combined therapy at DL2 develop DLT, then DL2 will be used for part 2 (expansion cohort). If 1 patient out of the 3 patients has DLT at DL2, we will expand cohort to 3 more patients and if 1 patient of the 6 patients has DLT (i.e only 0/3 or 1/6), dose level 2

(DL2) will be used for part 2 (expansion cohort). If 2 or more patients of the 6 patients have DLT, DL1 will be used for expansion cohort.

An additional dose level (DL -1) in which day 8 of ENT will be omitted (i.e. ENT at 8mg on D1, and Pembrolizumab (MK-3475) at 200mg IV on D1 of 21-day cycles) will be used if 2 or more patients develop DLT during the first 2 cycles of combined therapy at DL1. If 0 or 1 patients of the 6 patients treated with combined therapy at DL-1 develop DLT then DL-1 will be used in the second part of the study. If 2 or more 6 patients enrolled in DL -1 develop DLT, then the study will be terminated.

Toxicities will be tabulated and graded according to the Common Terminology Criteria for Adverse Events Version 5 (CTCAE-5). DLT will be assessed after the first 2 cycles of combined therapy. Responses will be as defined by IWG-2006 criteria (CR, PR, or HI) and assessed at the end of cycle 1, the combined first 2 cycles, and every 2 cycles afterwards. Patients who achieve an objective response or maintain a stable disease (SD) status after the first 4 combination cycles will continue receiving both drugs at the same schedule till progression up to 1 year of combined therapy. Participants who do not complete the first 2 cycles of combined therapy without experiencing a DLT during dose escalation (as DLT period is defined in the first 2 combined therapy cycles) will also be replaced. To be DLT-evaluable, the patient must complete the first two cycles of combined therapy without experiencing a DLT. Any patient who is dose reduced during the entinostat run-in first cycle due to entinostat-related toxicity will be analyzed on the dose level that corresponds to the reduced dose level delivered during the first cycle of combined therapy.

PART 2: After the safe dose of the combination is established, 15 patients will be treated with ENT+ Pembrolizumab (MK-3475) combination at that same dose and schedule.

Assessment of response will occur after 4 combination cycles and similar to part 1, those who achieve an objective response or SD will continue to receive the therapy till progression. Patients who progress or respond and subsequently lose response will be withdrawn from study. BM biopsy/aspirate and PB samples will be done at baseline, after first cycle of ENT monotherapy, every 2 cycles of combined therapy, and at time of progression or study discontinuation. Formal safety assessment will be performed after the first 6 patients are enrolled and each have received at least 5 cycles (i.e. 1 ENT monotherapy cycle and 4 cycles of combined therapy (DL1, DL2) for each patient) to assess for any unexpected autoimmune or other toxicity.

Primary Endpoint(s): MTD will be defined by the occurrence of DLT among 2 dose schedules (see section 5.2)

Definitions of DLT: see section 5.2

The following early stopping rule for excess toxicity in the expansion cohort will be used: We will cease enrollment in the expansion phase at the dose determined from dose escalation part of the study if we observe two or more DLTs among the first six evaluable patients enrolled in the expansion cohort. An evaluable patient is any patient who received a study drug. If the true toxicity rate is 50% or greater at the MTD then this rule will stop the trial with probability at least .89. Similarly, if the true toxicity rate is 33% at the MTD then this stopping rule will end the trial with probability .65. In that event, a new expansion cohort will

start at the dose level immediately below the dose level that was expanded. If the dose level being expanded is dose level -1, then the study will be terminated.

Secondary Endpoint(s): Overall response rate (CR, PR, and HI) as defined by the modified International working group 2006 (IWG-2006) criteria for CR, PR, HI ([Appendix A1](#) and [Appendix A2](#)) with at least 15% to be continued

Exploratory Endpoint(s):

- Median response duration for responders, median time of progression to AML, median overall survival (OS) and 1- and 2-year OS rate
- Assessment of the dynamic quantitative change in proportion of MDSCs in BM with combined therapy (target of reducing to <10%) and correlation with any observed clinical responses

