5.1.3 Other Modality(ies) or Procedures: N/A

5.2 **Definition of Dose-Limiting Toxicity**

The primary endpoint is the maximum tolerated dose (MTD), which is the highest dose level where 1 or fewer of 6 participants experience a dose limiting toxicity (DLT) during the first two combined cycles of treatment. The recommend phase 2 dose (RP2D) is the same as the MTD.

NCI Protocol #:10009

Version Date: 09/04/2020

The maximally administered dose is the dose at which two or more of 6 participants experience a

DLT.

DLT will be defined as the occurrence of any of the following during the first 2 cycles of combined therapy unless the event can clearly be determined to be unrelated to the study drugs.

- Any grade 3 or 4 non-hematologic toxicity with the following exceptions: A) Transient laboratory abnormalities that can be treated or resolve to grade 2 or less within 72 hours.
- Grade 4 hematologic toxicity, including treatment-associated aplasia lasting >42 days from the last dose of study drug. Given that severe anemia, neutropenia and thrombocytopenia are features of advanced MDS and commonly encountered in this patient population, they will not be used to define DLT except if associated with prolonged treatment-associated aplasia as described above.
- Patients with grade 3 immune related adverse events will be removed from the treatment and this will be considered to be a DLT as well as any other immune-related adverse event that results in pembrolizumab interruption, dose modification, or discontinuation of therapy.

Participants who do not complete the first 2 cycles of combined therapy without experiencing a DLT (as DLT period is defined in the first 2 combined therapy cycles) during dose escalation will also be replaced. To be DLT-evaluable, the patient must complete the first two cycles of combined therapy without experiencing a DLT. Any patient who is dose reduced during the entinostat run-in first cycle due to entinostat-related toxicity will be analyzed on the dose level that corresponds to the reduced dose level delivered during the first cycle of combined therapy.

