A safety committee that includes the study chair, the principal investigator from any study site that has enrolled a patient on the specific DL, as well as two sub-investigators from Yale will review safety data after enrollment of every 3 patients during the dose escalation phase. The committee will have the discretion to decide to enroll 3 more patients in the specific dose level even if no DLT occurred in the first 3 treated patients in that dose level if there are toxicity/safety concerns that did not qualify as DLT (maximum of 6 evaluable patients to be enrolled at any dose level). The committee can also decide to enroll patients at a lower dose level after the first 3 or after the first 6 patients enrolled in any dose level even if no or one DLT occurred at that dose level if there are toxicity/safety concerns that did not qualify as DLT. The following regarding enrollment in different dose levels will be considered guidance for the safety committee but can be modified in accordance of above. Dose escalation will proceed within each cohort according to the following scheme.

Number of Patients with DLT at a Given Dose Level	Escalation Decision Rule
0 out of 3	Enter 3 patients at the next dose level.
≥ 2	Dose escalation will be stopped. This dose level will be declared the maximally administered dose (highest dose administered). Three (3) additional patients will be entered at the next lowest dose level if only 3 patients

	were treated previously at that dose.
1 out of 3	
Enter at least 3 more patients at this dose level.
 
• If 0 of these 3 patients experience DLT, proceed to the next dose level.• If 1 or more of this group suffer DLT, then dose escalation is stopped, and this dose is declared the maximally administered dose. Three (3) additional patients will be entered at the next lowest dose level if only 3 patients were treated previously at that dose.
≤ 1 out of 6 at highest dose level below the maximally administered dose	This is generally the recommended phase 2 dose (RP2D)= MTD. At least 6 patients must be entered at the recommended phase 2 dose (RP2D).

Management and dose modifications associated with the above adverse events are outlined in [Section 6](#).

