13.2 Sample Size/Accrual Rate

We expect to accrue 1-2 patients with MDS per month once the study is open.

Currently there is no therapy that has been shown to prolong survival in MDS in the post-DNMTi setting and that the expected best response in patients receiving supportive care only in post-DNMTi setting is negligible (1% or less). It is generally accepted that a $\geq 15\%$ ORR in the post-DNMTi is clinically meaningful and would be worth further evaluation in larger studies.

The total number of patients enrolled in the study will range from 21 to 27. The null hypothesis response rate of 1% (only supportive care) will be rejected if we observe 2 or more favorable responses. These criterion has significance level between .02 and .03 using a one-sided binomial test. This criterion has power between .84 and .93 for testing an alternative response rate of 15% with the combination therapy. Therefore, we will treat a total of 21 patients in the combination arm (6 in the first part of the study and 15 in the second part of the study).

DOMESTIC PLANNED ENROLLMENT REPORT						
Racial Categories	Ethnic Categories				Total	
	Not Hispanic or Latino		Hispanic or Latino			
	Female	Male	Female	Male		
American Indian/ Alaska Native	1	1	1	1	4	
Asian	1	1	0	0	2	
Native Hawaiian or Other Pacific Islander	1	0	0	0	1	
Black or African American	1	1	1	1	4	
White	4	4	1	1	10	
More Than One Race	0	0	0	0		
Total	8	7	3	3	21	

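### The escalation narrative can open Part 2 at a dose level with three treated patients, while Section 5.2 bases the MTD and RP2D on six

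*Combined protocol and SAP*

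**What the plan says.** **Narrative (synopsis, Section 5.1, Section 13.1).** No DLT in three patients at DL1 is enough to move to DL2. At DL2: "If no patient of the 3 patients treated with combined therapy at DL2 develop DLT, then DL2 will be used for part 2". If two or more of six have a DLT at DL2, "DL1 will be used for expansion cohort", with no condition on how many patients DL1 has had. At DL-1 the same narrative works with six patients. These rules are described as guidance that the safety committee may modify.

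**Section 5.2.** The MTD is the level "which is the highest dose level where 1 or fewer of 6 participants experience a dose limiting toxicity (DLT" (closing bracket omitted), counted over the first two combined cycles. "The recommend phase 2 dose (RP2D) is the same as the MTD". The escalation table adds: "At least 6 patients must be entered at the recommended phase 2 dose (RP2D" (bracket again omitted). When a level fails: "Three (3) additional patients will be entered at the next lowest dose level if only 3 patients" had been treated there.

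**Section 5.3.** The 15 expansion patients are added after the RP2D has been reached. DLT monitoring continues, and enrolment at that dose stops if two or more of the first six have a DLT.

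**Section 13.2.** Total enrolment is 21 to 27. "Therefore, we will treat a total of 21 patients in the combination arm (6 in the first part of the study"; the remaining 15 belong to Part 2.

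**The concern.** The MTD is the primary endpoint, and two current sets of rules for reaching it disagree. After 0/3 at DL1 and 0/3 at DL2, the narrative opens Part 2 at DL2 with three patients there. Under the Section 5.2 definition the MTD has not yet been established. After 0/3 at DL1 and failure at DL2, the narrative opens Part 2 at DL1, while the Section 5.2 table first asks for three more patients at DL1.

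The table does not settle the DL2 case. Its row for 0/3 points to a next level, and DL2 is the highest. Its RP2D row concerns the level below the maximally administered dose, and no such level exists if DL2 is tolerated. Sites or committee members working from different sections could act differently on identical data.

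**Working it through.** **1. The plan's own figures.**
- Expansion stop, 1 − q⁶ − 6pq⁵ with q = 1 − p: .8906 at p = .5 (stated .89) and .6488 at p = 1/3 (stated .65; at p = .33 exactly it is .642).
- Response rule, 2 or more responses, 1% against 15%: n = 21 gives significance level .0185 and power .845; n = 27 gives .0297 and .928. These agree with the stated .02 to .03 and .84 to .93.
- Enrolment: following every path of the narrative, and treating two or more DLTs in the first three as failure of the level, Part 1 takes 6 to 12 patients. Adding 15 gives 21 to 27, as stated. The minimum of 21 arises only when the expanded level has had three patients (0/3 then 0/3, or 0/3 at DL1 then two or more DLTs in three at DL2). The three-patient routes are therefore built into Section 13.2.

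**2. Enrolment if six are required before expansion.** The shortest path is 3 + 6 + 15 = 24. The longest is DL1 0/3, DL2 fails with six, DL1 is topped up to six and then fails, and DL-1 takes six: 6 + 6 + 6 + 15 = 33. At n = 33 the 2-response rule has significance level 1 − .99³³ − 33(.01)(.99³²) = 1 − .7177 − .2392 = .043, and power 1 − .85³³ − 33(.15)(.85³²) = 1 − .0047 − .0273 = .968. At n = 24 they are .024 and .894.

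A topped-up DL1 that then fails is uncommon. Its probability is q₁³ × P(2 or more DLTs in 3 at DL1) × P(DL2 fails). With assumed DLT rates of 10% at DL1 and 1/3 at DL2 this is .729 × .028 × .649 = .013. With 25% and 50% it is .422 × .156 × .891 = .059.

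**3. Chance that DL2 goes to expansion** (constant DLT rate p at DL2, independent patients, no committee override):
- narrative: q³ + 3pq² × q³
- six required: q⁶ + 6pq⁵
- passing the 2-of-6 stop as well: multiply either by q⁶ + 6pq⁵

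| p | Narrative | Six required | Narrative, after stop | Six, after stop |
|---|---|---|---|---|
| 1/3 | .2963 + .4444 × .2963 = .428 | .0878 + .2634 = .351 | .150 | .123 |
| .40 | .309 | .233 | .072 | .054 |
| .50 | .172 | .109 | .019 | .012 |

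At p = 1/3, .2963/.428 = 69% of the narrative's acceptances of DL2 rest on three patients.

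**4. One-sided 95% upper limits for the DLT rate.** After 0/3: 1 − .05^(1/3) = 63%. After 0/6: 1 − .05^(1/6) = 39%. After 1/6, which the definition also accepts: 58% (the p solving q⁶ + 6pq⁵ = .05).

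**5. The evaluability wording.** Sections 5.2, 5.3 and 13.1 call a patient DLT-evaluable only if two combined cycles are completed with no DLT. Read literally, no patient with a DLT is evaluable, and any six evaluable patients show 0/6. A count of at most 1 in 6 cannot be applied to that population.

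**The case against.** **The narrative is only guidance, and Part 2 is not the same as the MTD.** The narrative says which dose goes to Part 2; it does not say that this dose is declared the MTD, and Section 13.1 refers the primary endpoint to Section 5.2. This is fair, and it limits the point. A reader might infer that the plan names the MTD on three patients, or has no six-patient requirement. The documents do not support that, because Section 5.2 contains the requirement. What stands is the contradiction. The committee's discretion to add three patients after 0/3 is reserved for toxicity concerns, so it does not supply the default when there are none.

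**Expansion patients could make up the six.** Section 5.3 and Part 2 of Section 13.1 both start expansion after the dose is established. Patients enrolled because the RP2D is known cannot also establish it, unless the plan says so.

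**The 2-of-6 stop protects patients.** It does so in part, and it cuts the gap at one third from about 8 percentage points to under 3. It acts only after further patients are exposed at that dose, and it counts anyone who received a study drug, which differs from the DLT-evaluable population of Section 5.2.

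**Loss of power.** A reader might infer that with 3 + 15 = 18 patients at the RP2D, power falls to .78. Sections 13.2 and 13.5 do not support this. The test counts the whole combination arm, 3 + 3 + 15 = 21 on that path, and power is .845 as stated.

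**Conclusion.** The point holds as an internal contradiction in the rules that lead to the primary endpoint. It does not show that either escalation rule is wrong; that choice is the sponsor's.

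The effect on dose selection is moderate: .43 against .35 at a DLT rate of one third, .17 against .11 at 50%, and .150 against .123 at one third once the expansion stop is applied. Setting 63% (0/3) against 39% (0/6) alone would overstate the difference in evidence, because 1/6 also meets the definition and leaves an upper limit of 58%.

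It is also tempting to infer that requiring six would stay within the stated ceiling of 27. It would for most paths, but not when a topped-up DL1 then fails.

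These figures assume one constant DLT rate per level, independent patients, no replacements, no committee override and no restarted expansion cohort. The DLT rates are illustrative; the documents give no expected rate for the combination.

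**What to change.** 1. Reconcile the escalation narrative (synopsis, Sections 5.1 and 13.1) with the MTD definition (synopsis, Section 5.2), the Section 5.2 table and Section 5.3, so that one rule governs both declaring the MTD/RP2D and opening Part 2. Cover the two open cases: 0/3 at DL2, and failure at DL2 when DL1 has had three patients.
2. State whether expansion patients count toward the six.
3. Correct the definition of a DLT-evaluable patient so that patients who have a DLT are counted.
4. Make Section 13.2 and the synopsis match the rule kept. If six are required before expansion, the range becomes 24 to 33, and the significance level and power of the 2-response rule must be restated (.024 to .043 and .89 to .97 if all treated patients count).

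**Cost.** An amendment to the wording and to Section 13.2. If six are required, the affected paths usually need three more escalation patients. The delay is an assumed 3 to 5 months: 63 days of observation (three 21-day cycles) plus accrual of three patients at the stated 1 to 2 per month. If the three-patient routes are kept, no patients are added, but the MTD definition and the Section 5.2 table must be reworded to fit them.
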